4.2. Variable Definitions

The following variables will only be calculated if not reported on the eCRF.

4.2.1. Body Mass Index

Body mass index will be calculated as follows:

BMI $(kg/m^2) = [weight (kg)] / [height (m)]^2$.

4.2.2. Prior and Concomitant Medication

Prior medication is defined as any nonstudy medication started before the first application of study treatment.

Concomitant medication is defined as any nonstudy medication that is started accordingly:

- Before the date of first application of study treatment and is ongoing throughout the study or ends on/after the date of first application of study treatment.
- On/after the date of first application of study treatment and is ongoing or ends during the course of study treatment.

A prior medication could also be classified as "both prior and concomitant medication" if the end date is on or after the first application of study treatment. In the listing, it will be indicated whether a medication is prior-only, concomitant-only, or both prior and concomitant.

For the purposes of analysis, all medications will be considered concomitant medications unless the medications can unequivocally be defined as not concomitant.

5. STATISTICAL METHODOLOGY

5.1. General Methodology

Unless otherwise noted, SAS[®] software (SAS Institute Inc, Cary, NC; v9.1 or later) will be used for the generation of all tables, graphs, and statistical analyses. Descriptive summaries for continuous variables will include but not be limited to the number of observations, mean, STD, median, minimum, maximum, first quartile, third quartile, and 95% CI. Descriptive summaries for categorical variables will include the number and percentage of participants in each category.

5.2. Treatment Groups

This is a randomized, double-blind, vehicle-controlled study followed by an open-label treatment extension period. Data will be summarized based on the treatment regimen that was assigned at randomization (ITT population) or based on the treatment the participant actually applied on Day 1 (safety population).

During the double-blind period, the treatment groups will be ruxolitinib 1.5% cream BID and vehicle cream.

During the open-label treatment extension period, the treatment groups will be ruxolitinib 1.5% cream BID and vehicle cream to ruxolitinib 1.5% cream BID.

5.3. Analysis Populations

5.3.1. All-Screened Population

The all-screened population will include all participants who signed the informed consent form.

5.3.2. Intent-to-Treat Population

All participants who were randomized to the study will constitute the ITT population. Treatment groups for this population will be defined according to the treatment assignment at the time of randomization regardless of the actual study treatment the participant might apply during their participation in the study.

The ITT population will be used for the summary of demographics, baseline characteristics, participant disposition,

5.3.3. Safety Population

All randomized participants who applied ruxolitinib cream or vehicle cream at least once will constitute the safety population. Treatment groups for this population will be determined according to the actual treatment the participant applied on Day 1 regardless of assigned study treatment.

All safety analyses will be conducted using the safety population.

5.3.4. Treatment-Extension Evaluable Population

Participants who applied ruxolitinib cream at least once in the treatment extension period will constitute the TEE population. The TEE population will be used for summary of safety during the treatment extension period.

6. **BASELINE, EXPOSURE, AND DISPOSITION**

Appendix A provides a list of data displays. Sample data displays are included in a separate document.

6.1. Demographics, Baseline Characteristics, and Disease History

6.1.1. Demographics and Baseline Characteristics

The following demographics and baseline characteristics will be summarized for the ITT and TEE populations: age, age group, sex, race, ethnicity, region, weight, height, BMI, and skin type (Fitzpatrick scale Type I/II/III/IV/V/VI).

6.1.2. Baseline Disease Characteristics and Disease History

Baseline disease characteristics summarized for the ITT population include but are not limited to the following:

- Time since initial diagnosis of vitiligo
- Vitiligo diagnosed in childhood (No/Yes [age]: 0-5 years, 6-11 years, 12-17 years)
- Other autoimmune disorders
- Prior therapy given for vitiligo (predefined systemic treatments, phototherapy, and surgical procedures)
- History of acne vulgaris (No/Yes)
- Currently have acne vulgaris on the face (No/Yes)
- Vitiligo in genital area (No/Yes)

6.1.3. **Prior Therapy for Vitiligo**

Prior medication information for vitiligo will be used to identify other, non-predefined medication received by participants before enrollment into the study. Prior medications for vitiligo will be summarized by treatment group.

6.1.4. Medical History

For participants in the ITT population, medical history will be summarized by treatment group. This summary will include the number and percentage of participants with medical history for each SOC/PT as documented in the eCRF.

6.2. Disposition of Participants

The number and percentage of participants who were enrolled, who were randomized (double-blind period only), who were treated, and who completed treatment for each period will be summarized for the ITT and TEE populations. The number of participants enrolled by country and/or site will also be provided by treatment group.

6.3. **Protocol Deviations**

Protocol deviations will be summarized and listed.

6.4. Exposure

For participants in the safety population during the double-blind period and overall treatment period and for participants in the TEE population during the treatment extension period, descriptive statistics will be provided for duration of treatment, average daily dose, and total dose.

6.5. Study Drug Compliance

Overall compliance (%) for the application of ruxolitinib cream or vehicle cream during the double-blind period and overall treatment period (safety population) and ruxolitinib cream during the treatment extension period (TEE population) will be calculated for all participants as follows:

Overall application compliance (%) = $100 \times [\text{total number of nonmissing applications}] / [total number of intended applications]$

The total number of nonmissing applications is the total number of applications that the participant actually applied in each period during the study. The total number of intended applications is the number of planned applications minus the number of interrupted applications.

6.6. Prior and Concomitant Medication

Prior medications and concomitant medications will be coded using the WHO Drug Dictionary and summarized as the number and percentage of participants with prior and concomitant medications by WHO drug class and WHO drug term.

For participants in the ITT population, prior and concomitant medications will be summarized by treatment group as well as listed. For participants in the TEE population, concomitant medications will be summarized by treatment group as well as listed.

I

8. PHARMACODYNAMICS

Serum CXCL10 levels and skin biomarkers will be evaluated for percentage change from baseline at Week 4, Week 12, and Week 24. Likewise, a change from baseline in CXCL10 gene expression and skin biomarkers will be evaluated in skin samples at Week 12 and Week 24.

9. SAFETY AND TOLERABILITY

Appendix A provides a list data displays. Sample data displays are included in a separate document.

9.1. General Considerations

Summary tables may be replaced with listings when appropriate. For instance, an AE frequency table may be replaced with a listing if it only contains a few unique PTs reported on relatively few participants.

9.2. Adverse Events

9.2.1. Adverse Event Definitions

A TEAE is any AE either reported for the first time or worsening of a pre-existing event after the first application of study drug and within 30 days of the last application of study drug. For participants who cross over treatments, the first application date is period-specific, and the end date is 30 days after the last application date in the period, or the day before the first application date in the next period, whichever comes first. Analysis of AEs (as discussed below) will be limited to TEAEs, but data listings will include all AEs regardless of their timing in relation to study drug application.

Adverse events will be tabulated by MedDRA PT and SOC. Severity of AEs will be graded using the NCI CTCAE v5.0. The CTCAE reporting guidelines and grading details are available on the Cancer Therapy Evaluation Program website.

The subset of AEs considered by the investigator to be related to study drug will be considered to be treatment-related AEs. If the investigator does not specify the relationship of the AE to study drug, the AE will be considered to be treatment-related. The incidence of AEs and treatment-related AEs will be tabulated. Serious AEs will also be tabulated.

Any missing onset date, causality, or severity must be queried for resolution. Unresolved missing causality and severity will be handled according to the following rules:

- An unresolved missing causality will be considered treatment-related.
- An unresolved missing severity will be identified as an unknown severity.

For purposes of analysis, all AEs will be considered TEAEs unless the AE can unequivocally be defined as not treatment-emergent.

Application site reactions are AEs that occur at the site of study drug application. A summary of ASRs will be provided. Exposure-adjusted summaries will be provided for the safety population including cumulative TEAEs.

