Study Design	Randomized, double-blind, vehicle-controlled, with an open-label treatment extension.
Estimated Duration of Study Participation	Screening: Up to 42 days. Double-blind period: 24 weeks. Open-label period: 28 weeks. Safety follow-up: 30 days after last application of study drug or last study visit. Total: Up to approximately 63 weeks.
DSMB	No
Coordinating Principal Investigator	To be determined

Treatment Groups and Duration:

This is a randomized, double-blind, vehicle-controlled study with an open-label treatment extension period in adult participants (age ≥ 18 years) with nonsegmental vitiligo who have depigmented areas including $\geq 0.5\%$ BSA on the face, ≥ 0.5 F-VASI, $\geq 3\%$ BSA on nonfacial areas, and ≥ 3 T-VASI. Total body involved vitiligo area (facial and nonfacial) should not exceed 50% BSA. Approximately 60 participants will be randomized 2:1 to receive initial double-blind study treatment (ruxolitinib cream 1.5%:vehicle) administered BID for 24 weeks (see Figure 1). Participants will be stratified by age (≤ 40 years old and > 40 years old). During the double-blind treatment period, the participant's randomized treatment will be applied to depigmented areas on the face and body up to 20% T-BSA (facial and nonfacial).

After completion of the Week 24 assessments from the double-blind treatment period, eligible participants will be offered the opportunity to continue the study in the 28-week open-label treatment extension period in which all participants will receive open-label ruxolitinib cream 1.5%, administered BID. To be eligible for the open-label treatment extension period, participants must have completed the baseline and Week 24 visit assessments, be compliant with study procedures, and not have any safety issues. The total treated area in the open-label treatment extension period should not exceed 20% BSA (facial and nonfacial).

Figure 1 presents the study design schema. The SoA is detailed in Table 3 (for the double-blind treatment period) and Table 4 (for the open-label treatment extension period). Adherence to the study design requirements, including those specified in the SoA, is essential and required for study conduct.

Figure 1: Study Design Schema

	Screening	Double-Blind, Vehicle-Controlled Treatment			l Treatmen			
Procedure	Days -42 to -1	Day 1 (Baseline)	Wk 4 (± 3 d)	Wk 8 (± 3 d)	Wk 12 (± 3 d)	Wk 18 (± 7 d)	Wk 24 ^a (EOT1) (± 7 d)	Notes
Administrative procedures								
Informed consent	Х							

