Contact IRT	X*	Х	Х	Х	Х	Х	Х	*Entry of age into the IRT will be required at screening.
Inclusion and exclusion criteria	Х	Х						
Demography	Х							
General and disease medical history	Х							
Prior/concomitant medications	Х	X	Х	Х	Х	Х	X	
Application of study drug at site		Х	Х	X	Х	X	X*	At each study visit, starting at Day 1, the participant should apply the study drug under direct supervision of the site staff. *At the Week 24 visit, study drug is only applied by participants continuing in the open-label treatment extension period.
Dispense (D) and return (R) study drug and reminder/diary cards		D	R/D	R/D	R/D	R/D	R/D*	All tubes of study drug will be weighed before being dispensed. All returned tubes of study drug will be weighed. *At the Week 24 visit, study drug and diary cards are only dispensed to participants continuing in the open-label treatment extension period.
Collect study drug and collect/review study drug diary cards			Х	Х	Х	Х	Х	
Assess compliance			Х	Х	Х	Х	Х	

Table 3: Schedule of Activities: Double-Blind, Vehicle-Controlled Treatment Period (Day 1 to Week 24)

	Screening	Double-Blind, Vehicle-Controlled Treatment				l Treatmen		
Procedure	Days -42 to -1	Day 1 (Baseline)	Wk 4 (± 3 d)	Wk 8 (± 3 d)	Wk 12 (± 3 d)	Wk 18 (± 7 d)	Wk 24 ^a (EOT1) (± 7 d)	Notes
Safety assessments		· · · ·	,	,	,	,	. ,	
AE assessment	Х	Х	Х	Х	Х	Х	Х	
Comprehensive physical examination	Х						Х	
Targeted physical examination		X	X	X	Х	Х		See Section 8.3.2.
Vital signs	Х	Х	Х	Х	Х	Х	Х	
12-Lead ECG	Х							12-Lead ECG performed within 2 months before baseline is acceptable.
Laboratory assessments								
Hematology and chemistry assessments	Х	X	X	X	Х	Х	X	
Serology	Х							Serology includes hepatitis and HIV assessments.
Thyroid testing	Х							
Urinalysis	Х							
FSH	X*							*FSH is only measured for confirmation of nonchildbearing status of women who are postmenopausal, defined as having amenorrhea for at least 12 months without an alternative medical cause before screening.
Pregnancy testing	X*	X	X	X	X	X	X	*Female participants of childbearing potential will have a serum test at the screening and safety follow-up visits. A urine test will be conducted at all other visits. A positive urine test must be confirmed by a serum test.

Table 3: Schedule of Activities: Double-Blind, Vehicle-Controlled Treatment Period (Day 1 to Week 24) (Continued)

Table 3: Schedule of Activities: Double-Blind, Vehicle-Controlled Treatment Period (Day 1 to Week 24) (Continued)

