	Screening	Double-Blind, Vehicle-Controlled Treatment			l Treatmen			
							Wk 24 ^a	
	Days	Day 1	Wk 4	Wk 8	Wk 12	Wk 18	(EOT1)	
Procedure	-42 to -1	(Baseline)	(± 3 d)	(± 3 d)	(± 3 d)	(± 7 d)	(± 7 d)	Notes
translational assessm	ents							
Serum biomarker compling		v	v		v		v	
Seruin biomarker sampling		Λ	Λ		Λ		Λ	
_						1		
Skin biopsy: lesional vitiligo		Х			Х		Х	For lesional skin, per timepoint will be taken
skin (identified at baseline								from the inside edge of an active vitiligo lesion, and the
[Day 1])								sampling area should be entirely contained within lesional
								skin.
								See Section 8.5.1.
Skin biopsy: nonlesional		Х						For nonlesional skin, will be taken at baseline
								(Day 1) from uninvolved skin adjacent to the lesional area
								selected for biopsy.

Note: Unscheduled visits may occur at any time at the investigator's discretion, and appropriate clinical and laboratory tests may be performed, as clinically indicated.

^a Week 24 is considered the first visit of the open-label period.

Table 4: Schedule of Activities: Open-Label Treatment Extension (Week 28 to Week 52)

	Open-Label Treatment Extension		Safety Follow-Up		
Procedure	Wk 28	Wk 40	Wk 52 (EOT2 ^a)	30 Days After EOT1/EOT2 ^b (EOS) (+ 7 d)	Notes
Administrative procedures	(± / u)	(± / u)	(± / u)	(† 7 u)	110105
Contact IRT	X	X	x	X	
Prior/concomitant medications	X	X	X	X	
Application of study drug at site	Х	Х			At each study visit, the participant should apply the study drug under direct supervision of the site staff.
Dispense (D) and return (R) study drug and reminder/diary cards	R/D	R/D	R		All tubes of study drug will be weighed before being dispensed. All returned tubes of study drug will be weighed.
Collect study drug and collect/ review study drug diary cards	Х	Х	Х		
Assess compliance	Х	Х	Х		
Safety assessments					
AE assessment	Х	Х	Х	Х	
Comprehensive physical examination			Х		
Targeted physical examination	Х	Х		Х	See Section 8.3.2.
Vital signs	Х	Х	Х	Х	
- · · · · · · · · · · · · · · · · · · ·					
Laboratory assessments					
Hematology and chemistry assessments	Х	Х	Х	Х	
Pregnancy testing	Х	Х	Х	X*	*Female participants of childbearing potential will have a serum test at the screening and safety follow-up visits. A urine test will be conducted at all other visits. A positive urine test must be confirmed by a serum test.
translational assessments	5				

Table 4: Schedule of Activities: Open-Label Treatment Extension (Week 28 to Week 52) (Continued)

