6.1. Study Treatments Administered

Table 6 presents the study treatment information.

Table 6:Study Treatment Information

	Ruxolitinib	Vehicle		
Study treatment name:				
MOA:	Inhibitor of the JAK family of protein tyrosine kinases	Not applicable		
Dosage formulation:	Cre	eam		
Unit dose strength(s)/dosage level(s):	1.5%	Not applicable		
Route of administration:	Topical			
Administration instructions:	A thin film is applied BID to depigmented vitiligo areas on the face and body up to 20% T-BSA.			
Packaging and labeling:	Ruxolitinib cream and vehicle cream will be provided in 60 g tubes. Each tube will be labeled as required per country requirement.			
Storage:	Ambient (15°C-30°C/59°F-86°F)			
Status of treatment in participating countries:	Investigational	Not applicable		

The application of study drug will be limited to $\leq 20\%$ of the participant's T-BSA, regardless of whether the participant has depigmentation on > 20% BSA. For participants with depigmentation on > 20% BSA, the investigator will discuss with the participant at baseline (Day 1) which areas of vitiligo to treat, and the areas selected for treatment must include all areas in which skin biopsies will be performed. The site should document the area to be treated in the eCRF.

All tubes of study drug will be weighed before being dispensed. All returned tubes of study drug will also be weighed.

Study drug will be applied as a thin film BID, with applications at least 8 hours apart. Participants should remove study drug from the tube in fingertip units until all of the areas to be treated are covered by a thin film.

Participants will be instructed to document treated areas and advised to limit use to no more than 1 tube (60 g) per 3-4 days. Application instructions will be provided by the site study staff, and the participants will record their daily applications via a diary card given to the participants during each study visit. Refer to the Study Pharmacy Manual for participant instructions for handling of study drug.

On the day of a visit, the participant should not apply their morning dose of study drug at home; instead, study drug will be applied from a new kit in the clinic during the visit, under direct supervision of the site staff. The tube will be weighed before and after application to determine the participant's dosage.

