3.2.11.1.X	Summary of Treatment-Emergent Adverse Events Leading to Discontinuation of Study Drug by MedDRA System Organ Class and Preferred Term	Safety/TEE
Laboratory values and vital signs		
3.3.1.X	Summary of Laboratory Values – Hematology	Safety/TEE
3.3.3.X	Shift Summary of Hematology Laboratory Values in CTCAE Grade – To the Worst Abnormal Value	Safety/TEE
3.3.4.X	Summary of Laboratory Values – Chemistry	Safety/TEE
3.3.6.X	Shift Summary of Chemistry Laboratory Values in CTCAE Grade – To the Worst Abnormal Value	Safety/TEE
3.4.1.X	Summary of Systolic Blood Pressure	Safety/TEE
3.4.2.X	Summary of Diastolic Blood Pressure	Safety/TEE
3.4.3.X	Summary of Pulse	Safety/TEE
3.4.4.X	Summary of Respiration Rate	Safety/TEE
3.4.5.X	Summary of Body Temperature	Safety/TEE

Note: For AE tables ending with X, separate tables will be provided for the double-blind period (safety population) and treatment extension period (TEE population).

Note: For AE tables ending with Y, tables will be provided for the overall treatment period (double-blind and treatment extension periods). Participants who cross over should be included in both treatment groups.

Note: For laboratory values/vital sign tables ending with X, separate tables will be provided for the double-blind period (safety population) and treatment extension period (TEE population).

Listings

Listing No.	Title		
Demographic and baseline characteristics			
2.1.1	Participant Enrollment and Disposition Status		
2.1.2	Participants Who Discontinued Treatment or Discontinued From Study Due to COVID-19		
2.1.3	Participants With Assessments Not Done Due to COVID-19 Pandemic		
2.2.1	Protocol Deviations		
2.2.2	Participant Inclusion and Exclusion Criteria Violations		
2.3	Analysis Populations		
2.4.1	Demographic Characteristics		
2.4.2	Baseline Disease Characteristics		
2.4.3	Medical History		
2.4.4	Prior and Concomitant Medications		
2.4.5	Prior Medications for Vitiligo		
2.5.1	Study Drug Exposure and Compliance		
-			
-			
Adverse even	ts		
2.7.1	Adverse Events		
2.7.2	Adverse Events Leading to Study Drug Discontinuation		
2.7.3	Serious Adverse Events		
2.7.4	Treatment-Related Adverse Events		
2.7.5	Adverse Events With a Fatal Outcome		
2.7.6	Adverse Events Leading to Interruption of Study Drug		
2.7.8	Grade 3 or Higher Adverse Events		
2.7.9	Application Site Reactions		
Laboratory d	lata		
2.8.1.1	Clinical Laboratory Values – Hematology		
2.8.1.2	Clinical Laboratory Values – Chemistry		

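### SAP 9.2.1 closes a crossover participant's double-blind AE window the day before the Week 24 visit, so a finding made at that visit before open-label dosing drops out of the vehicle column

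*SAP*

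**What the plan says.** **The window.** SAP 9.2.1 counts an AE as treatment-emergent if it begins or worsens after the first application and within 30 days of the last. For participants who cross over, "the first application date is period-specific, and the end date is 30 days after the last application date in the period". A second limit can close the window sooner, and the earlier of the two governs: "or the day before the first application date in the next period, whichever comes first". Where timing is in doubt, "all AEs will be considered TEAEs unless the AE can unequivocally be defined as not treatment-emergent".

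**The switch.** Protocol Table 3 has continuing participants dosed in clinic at Week 24: "At the Week 24 visit, study drug is only applied by participants continuing in the open-label treatment extension period". Protocol 6.1 rules out a home dose on the morning of a visit; instead, "study drug will be applied from a new kit in the clinic during the visit, under direct supervision of the site staff". Protocol 8.1.4 places this application after the safety blood draws. The protocol summary and Protocol 4.1 offer the extension "After completion of the Week 24 assessments from the double-blind treatment period". Footnote a to Table 3 labels the same visit differently: "Week 24 is considered the first visit of the open-label period".

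**The tables.** SAP Appendix A plans separate AE tables for the double-blind and extension periods, plus overall-period tables, for which it says: "Participants who cross over should be included in both treatment groups".

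**The concern.** A cut on the day before the switch is harmless if everything done on the switch day follows the new drug. Here the order is reversed. Week 24 includes an AE review, vital signs, haematology, chemistry and the only post-baseline comprehensive examination of the double-blind period. All of these are described as double-blind assessments, and the open-label dose follows them on the same date.

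These assessments can generate AEs. Protocol 9.1, 8.3.2 and 8.3.3 make clinically meaningful laboratory and examination findings, and clinically significant vital signs, reportable. For something first detected at a visit, the visit date is a natural onset date.

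The frequency and severity of AEs is a secondary endpoint, and the double-blind period is the only randomised safety comparison. A vehicle-period finding that leaves the vehicle column, and may reappear under ruxolitinib, is misplaced by a written rule rather than by chance. With about 20 vehicle participants, one such case would be visible in the table.

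**Working it through.** The plan gives no figure for this point, so there is none to reproduce. The check is to apply the rule to dates.

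**Inputs from the documents**
- Window rule and default for unclear timing: SAP 9.2.1.
- First open-label application at the Week 24 visit, with a visit window of ± 7 days: Protocol Table 3.
- AE timing recorded as start and end dates, with no clock time listed: Protocol 9.3.
- Vehicle arm, n = 20: SAP Figure 1.

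**Assumptions**
- The Week 24 target is Day 24 × 7 + 1 = 169.
- The last vehicle dose is the day before the visit.
- A finding first made at the visit is dated to the visit.

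**Rule**

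End of vehicle window = min(last vehicle application + 30, first open-label application − 1)

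| Week 24 visit | Last vehicle dose + 30 | Day before open-label dose | Window ends | Onset on visit day |
|---|---|---|---|---|
| Day 162 | 161 + 30 = 191 | 161 | 161 | outside vehicle |
| Day 169 | 168 + 30 = 198 | 168 | 168 | outside vehicle |
| Day 176 | 175 + 30 = 205 | 175 | 175 | outside vehicle |

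The 30-day limb never decides the outcome when open-label dosing starts at the visit. An onset one day earlier (Day 168 for an on-target visit) stays with vehicle.

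**Where the excluded event goes**
1. If the record does not show whether it came before or after the dose, its date equals the first open-label date. The default makes it an extension TEAE. It then appears under vehicle-to-ruxolitinib in the extension tables and under ruxolitinib in the overall-period tables.
2. If it is shown to precede the dose, it did not arise after the first open-label application and is not an extension TEAE. It is also outside the vehicle window, so it is counted in neither period and survives only in the listings.

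It is lost from the vehicle column in both cases.

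**Illustration (assumed counts)**

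One participant of 20 is 1/20 = 5 percentage points. If 8/20 (40%) had a TEAE and one of those had only a pre-dose Week 24 finding, the table would show 7/20 (35%). Two such participants would be 2/20 = 10 points.

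**The case against.** **Only one date is affected.** This stands. The rule acts on onset dates, so AEs elicited at Week 24 with earlier onset remain vehicle events. Laboratory and vital-sign values are summarised by visit under SAP 9.3 and 10, and 9.2.1 does not assign them. A reader might infer that the vehicle arm loses one of its five post-baseline safety visits (Weeks 4, 8, 12, 18, 24), or 20% of its events. The documents do not support that: one calendar day of about 169 is cut. Neither fraction estimates the share of AEs involved.

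**Counting under ruxolitinib is not certain.** This also stands. It follows only where the order is not shown; otherwise the event falls between the two periods.

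**Extension entry requires no safety issues.** This limits the effect. A participant barred from the extension has no next period, so the event stays within 30 days of the last vehicle application. Findings judged compatible with continuing remain exposed. So may laboratory abnormalities from the central laboratory if results return after dosing; the documents give no turnaround time.

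**The asymmetry between arms is unproven.** This stands. The cut is written for participants who cross over, which the documents say only of vehicle participants. On that literal reading only the vehicle window is shortened. But SAP 4.1.1 makes Day 1 period-specific, and Appendix A plans AE tables by period for both arms. Some cut must therefore apply to ruxolitinib continuers, and the SAP does not state it. Bias between arms is something a reader might infer, not something the text establishes.

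**Some material is unavailable.** The CRFs and eCRF guidelines are not public, and SAP 9.2.2 does not appear in the available text. Any of them might capture the order of events. Even so, a captured order would not repair the stated vehicle cut-off. It would only move the event from the first outcome above to the second.

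**Conclusion.** The point holds in a limited form. By the stated rule, an AE found by a pre-application Week 24 assessment and dated that day is excluded from the vehicle column for anyone who crosses over. This holds across the whole visit window. Its later placement, under ruxolitinib or nowhere, depends on whether the order can be shown.

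The size cannot be estimated without AE rates. The 5-point shift per participant assumes 20 vehicle participants and a person with no other double-blind TEAE. The number exposed is at most the vehicle participants who continue. If only the vehicle window is cut, vehicle incidence is biased down, and ruxolitinib incidence up where the default applies. If both arms are cut on the same date, the asymmetry between windows goes, but vehicle findings can still be counted under ruxolitinib. Safety is descriptive with no alpha control, and the listings show every AE, so no formal test is affected. The correction is still worthwhile because it is cheap and the misplacement is foreseeable from the visit design.

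**What to change.** - In SAP 9.2.1, state that AEs arising from Week 24 assessments performed before the first open-label application belong to the double-blind period.
- State the cut date for ruxolitinib participants who continue, and apply the same cut and the same exception in both arms.
- Leave same-date events of unknown order under the existing date rule. Moving all of them to the double-blind period would risk counting reactions to the first open-label dose as vehicle events, which trades one error for another.
- Reconcile Table 3 footnote a with the protocol summary and Protocol 4.1, which treat the Week 24 assessments as double-blind.

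The cost is one SAP sentence on the window, one on the cut in the ruxolitinib arm, and one programming rule. Someone must also identify, from visit or sample records, which same-date AEs came from pre-application assessments. For laboratory findings Protocol 8.1.4 already fixes the order. For examination and vital signs the order rests on the statement that the Week 24 assessments are completed first.
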